8.3.6 SERIOUS ADVERSE EVENT REPORTING

Any AE that meets any criterion for a SAE requires the completion of an SAE Report Form in addition to being recorded on the AE pages of the CRF. The principal investigator is required to ensure that the data on these forms is accurate and consistent. This applies to all SAEs, regardless of relationship to study intervention, that occur after informed consent has been obtained.

All SAEs regardless of relatedness of expectedness will be reported immediately (within 48 hours of the principal investigators' knowledge of the event) to the NIAMS and the Data and Safety Monitoring Officer through the Executive Secretary (KAI).

The SAE report must provide a detailed description of the SAE. If a subject has died and an autopsy has been performed, copies of the autopsy report and death certificate will be sent to the NIAMS and Data and Safety Monitoring Board (DSMB) as soon as the information becomes available. Any follow-up data will be detailed in a subsequent SAE Report Form and sent to the NIAMS and DSMB accordingly.

The principal investigator or designee is responsible for informing the Institutional Review Board/Ethics Committee (IRB/IEC) of the SAE and providing them with all relevant initial and follow-up information about the event. The principal investigator or designee will keep copies of all SAE information, including correspondence with the NIAMS, DSMB and the IRB, on file. All SAEs that have not resolved upon discontinuation of the subject's participation in the study will be followed until either the event resolves completely, stabilizes/resolves with sequelae, or returns to baseline (if a baseline value is available).

8.3.7 REPORTING EVENTS TO PARTICIPANTS

If any adverse or serious adverse event results in a change to the risk/benefit ratio of the study, participants will be notified immediately, and asked to re-consent to participating in the study by signing an updated informed consent form

8.4 UNANTICIPATED PROBLEMS

8.4.1 DEFINITION OF UNANTICIPATED PROBLEMS (UPs)

The Office for Human Research Protections (OHRP) considers unanticipated problems involving risks to participants or others to include, in general, any incident, experience, or outcome that meets all of the following criteria:

• Unexpected in terms of nature, severity, or frequency given (a) the research procedures that are described in the protocol-related documents, such as the Institutional Review Board (IRB)- approved research protocol and informed consent document; and (b) the characteristics of the participant population being studied;

- Related or possibly related to participation in the research ("possibly related" means there is a reasonable possibility that the incident, experience, or outcome may have been caused by the procedures involved in the research); and
- Suggests that the research places participants or others at a greater risk of harm (including physical, psychological, economic, or social harm) than was previously known or recognized.

8.4.2 UNANTICIPATED PROBLEM REPORTING

The principal investigator will report unanticipated problems (UPs) to the reviewing Institutional Review Board (IRB) and to the NIAMS Data and Safety Monitoring Board (DSMB). The UP report will include the following information:

- Protocol identifying information: protocol title and number, PI's name, and the IRB project number;
- A detailed description of the event, incident, experience, or outcome;
- An explanation of the basis for determining that the event, incident, experience, or outcome represents an UP;
- A description of any changes to the protocol or other corrective actions that have been taken or are proposed in response to the UP.

To satisfy the requirement for prompt reporting, UPs will be reported using the following timeline:

- UPs that are serious adverse events (SAEs) will be reported to the IRB and to the NIAMS and DSMB through the Executive Secretary (KAI) within **48 hours** of the investigator becoming aware of the event.
- Any other UP will be reported to the IRB and to the NIAMS DSMB within **10 working days** of the investigator becoming aware of the problem.
- All UPs should be reported to appropriate institutional officials (as required by an institution's written reporting procedures), the supporting agency head (or designee), and the Office for Human Research Protections (OHRP) within **10 working days** of the IRB's receipt of the report of the problem from the investigator.

8.4.3 REPORTING UNANTICIPATED PROBLEMS TO PARTICIPANTS

Participants will be notified of any unanticipated problems via emailed letter from the Principal Investigator.

9 STATISTICAL CONSIDERATIONS

9.1 SAMPLE SIZE DETERMINATION

We consider $\delta_U = \pm 6.5$ as the equivalence limit for our primary outcome, SA-EASI, which is half of a clinically significant difference and much more conservative than prior studies.¹¹ We computed sample size estimates for equivalency comparison of means for the primary endpoint and secondary endpoints from Aim 1 and Aim 2 using one-sided $\alpha = 0.05$ and 80% power (PASS version 14). 272 patients randomized are sufficient to determine equivalency with 80% power for the primary endpoint of EASI given the range of SD (15-20), with anticipated 15% attrition. This N is larger than that required for any

of the other outcomes.²³⁻²⁵ Thus, enrolling 300 patients provides adequate power to evaluate primary and all secondary outcomes and accounts for attrition.

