3 OBJECTIVES AND ENDPOINTS

OBJECTIVES	ENDPOINTS	JUSTIFICATION FOR ENDPOINTS
Primary		
Aim 1: Compare differences in atopic dermatitis disease severity, as measured by Eczema Area and Severity Index (EASI), and validated Investigator Global Assessment (vIGA), and Patient-Oriented Eczema Measure (POEM) between patients randomized to TCH and in-person care in a 12-month pragmatic, randomized equivalency trial.	 The primary endpoint of the study is the mean improvement from baseline in EASI averaged across 12 months. The mean improvement in EASI is defined as the difference in EASI between baseline and the average of the follow-up visits (months 3-12). Secondary endpoints for Aim 1 include: Change in vIGA from baseline averaged across 12 months Change in POEM from baseline averaged across 12 months 	EASI is a validated, granular assessment of AD patient disease severity. It is commonly used in clinical trials, including trials for therapeutic approvals. By using EASI, we will be able to compare the results of this study with other studies in AD patients. The 5-point IGA is a valid measure of disease severity and meets the need for a clinically meaningful measure for atopic dermatitis. POEM is a validated patient-reported outcome used to

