9.3.2 ANALYSIS OF THE PRIMARY EFFICAY ENDPOINTS

The primary endpoint of the study is the mean improvement from baseline in EASI versus the follow-up visits (months 3-12). The comparison of improvement in EASI will incorporate all available post-intervention follow-up visits. Our primary goal will be to compare the mean difference in improvement between groups to examine if they are equivalent.

We will use an intent-to-treat (ITT) approach to evaluate equivalency of changes between the two arms across 12 months for AD-disease-severity and quality-of-life endpoints using longitudinal linear mixed modeling. This modeling allows us to account for intra-individual variability and the possibility of different numbers of follow-up measurements inherent in this pragmatic research design. For these analyses, the null hypothesis is that there is a differential treatment effect between the groups: H_0 : $\mu I_{n-person} \neq \mu_{TCH}$. The alternate hypothesis is H_A : $\mu_{In-person} = \mu_{TCH}$, where μ represents the average change from baseline across the follow-up visits (3 months – 12 months).

For the primary comparison of baseline versus average of follow-up visits, a dummy-coded time variable will be coded with 0 = baseline and 1 for all follow-up visits, so that the estimate of the effect will indicate the difference between baseline and the average of follow-up visits. In addition, a group

variable will be added to the model (coded 0 for in-person and 1 for TCH) along with a group x time effect.

We consider $\delta_0 = \pm 6.5$ as the equivalence limit for the primary endpoint of EASI. This equivalence limit of 6.5 was selected for EASI because it represents the minimal clinically important difference in the AD literature.²⁸ It is also more conservative than equivalency limits of 12-20 from pilot studies.²⁹

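### Section 9.1 claims 80% equivalence power over SD 15-20 without saying what the SD measures; read as the SD of the defined primary endpoint, 300 patients give 65-76% at SD 20

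*Combined protocol and SAP*

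**What the plan says.** Section 9.1 describes the calculation as an equivalence comparison: "We computed sample size estimates for equivalency comparison of means for the primary endpoint" and the secondary endpoints, at one-sided alpha 0.05 and 80% power. The margin is ±6.5, and Section 9.3.2 repeats it: "This equivalence limit of 6.5 was selected for EASI". The result is given as "272 patients randomized are sufficient to determine equivalency with 80% power for the primary endpoint of EASI given the range of SD (15-20"), with 15% attrition anticipated. Section 9.1 then concludes: "Thus, enrolling 300 patients provides adequate power to evaluate primary and all secondary outcomes and accounts for attrition".

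The endpoint is defined elsewhere. Section 3 states: "The mean improvement in EASI is defined as the difference in EASI between baseline and the average of the follow-up visits (months 3-12"). Section 9.3.2 codes time as 0 at baseline and 1 at every later visit, "so that the estimate of the effect will indicate the difference between baseline and the average of follow-up visits", and adds: "The comparison of improvement in EASI will incorporate all available post-intervention follow-up visits".

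Section 9.1 does not say which quantity has an SD of 15-20, what true difference was assumed, or whether both bounds entered the calculation. No within-patient correlation is given anywhere.

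**The concern.** The sentence attaches the SD to the primary endpoint, so the natural reading is the SD of the averaged change. An equivalence claim needs both one-sided tests to succeed, which takes more patients than a single one-sided test at the same margin. A figure of 272 looked too small for two bounds at SD 20.

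At stake is the chance that a truly equivalent online model ends with an inconclusive result. A reader of Section 9.1 would put that chance at no more than 20% anywhere in SD 15-20. If it is larger, an inconclusive trial could be misread as evidence against equivalence.

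**Working it through.** **Inputs.** Margin Δ = 6.5 (Sections 9.1, 9.3.2); one-sided alpha 0.05 at each bound, SD 15-20, 15% attrition, 272 and 300 randomised (Section 9.1); 1:1 allocation (Section 5.4.1). Assumed: SD is that of the averaged change; true difference 0, the most favourable value.

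**Where 272 could come from.** Patients per arm for 80% power:

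- Two bounds, true difference 0: n = 2·SD²·(1.645 + 1.282)²/Δ². SD 15 gives 92, SD 17 gives 118, SD 17.5 gives 125. SD 20 gives 2·400·8.564/42.25 = 162.2, so 163.
- One bound only: n = 2·SD²·(1.645 + 0.842)²/Δ². SD 20 gives 2·400·6.183/42.25 = 117.1, so 118.

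Then 118 × 2 × 1.15 = 271.4, which rounds up to 272. The same 118 per arm arises from one bound at SD 20 and from two bounds at SD 17, so the origin of 272 cannot be determined. Neither route gives two-bound power of 80% at SD 20.

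**Two-bound power.** The normal approximation is 2Φ(Δ/SE − 1.645) − 1 with SE = SD·√(2/n), n per arm. For 255 evaluable at SD 20: SE = 20·√(2/127.5) = 2.505; 6.5/2.505 = 2.595; 2Φ(0.950) − 1 = 65.8%. The table uses the t version, integrated over the sampling distribution of the variance.

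| Randomised | Evaluable | SD 15 | SD 17.5 | SD 20 | Largest SD with 80% |
|---|---|---|---|---|---|
| 300 | 255 (15% lost) | 92.9% | 81.1% | 65.4% | 17.69 |
| 300 | 300 (none lost) | 96.4% | 88.2% | 75.5% | 19.19 |
| 272 | 231 (15% lost) | 89.9% | 75.8% | 58.6% | 16.83 |
| 272 | 272 (none lost) | 94.5% | 84.2% | 69.6% | 18.27 |

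All four largest SDs lie below 20.

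**Non-zero true difference, 255 evaluable.** At SD 15 / 17.5 / 20, a difference of 1 gives 88.9 / 76.6 / 61.7%, and a difference of 2 gives 76.9 / 64.3 / 51.7%.

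**If SD 20 is on a single-visit basis.** The documents give no correlations, so these are illustrations only: equal variances at all visits, ρ = 0.5, 255 evaluable.

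- *Score, equal correlation.* Averaged-change SD = 20·√(1.25(1 − ρ)) = 15.81; power 89.7%. Power of 80% needs ρ of about 0.37.
- *Score, AR(1).* The variance factor is 1 + [4 + 2(3ρ + 2ρ² + ρ³)]/16 − (ρ + ρ² + ρ³ + ρ⁴)/2 = 1.0469, so SD = 20.46; power 62.4%. Power of 80% needs ρ of about 0.71.
- *Change, equal correlation.* SD = 20·√(1.25/2) = 15.81; power 89.7%.
- *Change, AR(1).* If SD 20 is that of the month-12 change, the averaged-change SD is 14.94 and power 93.1%. If it is that of the month-3 change, they are 20.46 and 62.4%.

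**The case against.** **The SD may be a single-visit figure, in which case there is no shortfall.** This stands as a possibility. The patient random effects in Section 9.3.1 point towards equal correlation, under which a single-visit score needs ρ of only about 0.37 at 255 evaluable. But the plan states neither the basis nor a correlation, and the illustrations run from 62% to 93%. The claim cannot be checked without inputs that are not in the document.

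**The true difference and the two bounds are implied.** Section 9.3.2 sets equality of the two mean changes as the alternative, and a ± margin with one-sided alpha is common shorthand for two one-sided tests. This partly stands. However, the hypotheses in Section 9.3.2 do not write out the bounds, and 272 also matches a one-bound calculation at SD 20, so the shorthand does not settle what was computed.

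**65% is the pessimistic end.** This stands. The mixed model keeps partial data. As an illustration, let dropout be spread evenly over the four visits to 15% by month 12, with equal correlation. A patient with k follow-up visits then carries 1.25/(1 + 1/k) of full information. Total information is 0.85 + 0.0375 × (0.9375 + 0.8333 + 0.625) = 0.94, equivalent to 282 patients. Power at SD 20 is about 72%, and 80% holds to SD of about 18.6. That is better than 65% but still short of the claim.

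**The consequences are small.** Largely true: 300 is adequate at mid-range, and no conduct or analysis decision changes. The plan nevertheless claims the whole range.

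**Conclusion.** The concern holds. With the SD read as that of the defined endpoint and a true difference of 0, 300 randomised give 65-76% two-bound power at SD 20, depending on how much information attrition removes. The 80% claim fails at the top of the range even with no attrition. A truly equivalent model would then have a 24-35% chance of an inconclusive result, against the 20% at most that Section 9.1 implies. Any non-zero true difference lowers power further.

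The shortfall is confined to the upper part of the range and depends on the SD's meaning. That the basis is unstated is certain; that power falls short is conditional on the averaged-change reading. The type I error rate is unaffected. This should be corrected, but it does not threaten the validity of the trial.

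**What to change.** In Section 9.1:

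1. State what SD 15-20 refers to (averaged change, single-visit score or single-visit change), the assumed true difference, and that both bounds are tested.
2. Replace the blanket 80% statement with two-bound power across SD 15-20 at the planned 300, on that basis.

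If the SD is that of the averaged change, suitable text is: *Taking the SD as that of the averaged change and a true difference of 0, 300 randomised (255 evaluable after 15% attrition) gives two-bound power of about 93% at SD 15, 81% at SD 17.5 and 65% at SD 20; 80% power holds for SD up to about 17.7. With no attrition the corresponding figures are 96%, 88% and 76%, and 80% power holds up to about SD 19.2.*

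If the SD is on a single-visit basis, state the assumed visit variances and correlation structure and recompute from them, with a range. A fixed conversion formula should not be used, because the answer depends on the structure.

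The cost is one recalculation and a few sentences. Enrolment stays at 300 and conduct is unchanged. The downside is a less favourable stated power at the top of the SD range if the averaged-change reading is the intended one.

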9.2 POPULATIONS FOR ANALYSES

We will use an intent-to-treat (ITT) approach to evaluate equivalency of changes between the two arms across 12 months for AD-disease-severity and quality-of-life endpoints using longitudinal linear mixed modeling.

9.3 STATISTICAL ANALYSES

9.3.1 GENERAL APPROACH

For this pragmatic, randomized trial, we will compare patients randomized to the online, team-based connected health (TCH) versus patients receiving in-person care across one year. The overall analytical strategy is to use linear mixed or generalized estimating equations, depending on the outcome variable, to account for repeated measures within patients. Random effects for patients will be included in the model so that the estimates of any patient-level variables will be appropriately calculated. Additionally, we will adjust *a priori* for the randomization stratification factors site and age group (<18 years, and 18+ years) in all models. While we do not anticipate a site-level main effect, random effects for site will be included in the model in case there are factors common to patients within a site that affect the outcome.

For comparison of AD disease severity (Aim 1) and quality of life (Aim 2), we will test an equivalence hypothesis between the interventions using longitudinal linear mixed effects modeling; this allows for the estimation of intra-individual variance. Using this same technique, we will test the hypothesis of improved access to specialist care (Aim 2) and cost-saving (Aim 3) with the TCH model compared to the in- person model.

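### The primary mixed model names patient random effects but no patient-level effect of time; fitted literally as a random intercept, it would give false equivalence of about 7% to 11% under assumed differences in response between patients

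*Combined protocol and SAP*

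**What the plan says.** Section 9.3.1 sets out linear mixed models or generalized estimating equations, depending on the outcome. On the patient level it says only: "Random effects for patients will be included in the model so that the estimates of any patient-level variables will be appropriately calculated". Random effects for site are added to absorb factors shared by patients at a site. The mixed model is justified on the ground that "this allows for the estimation of intra-individual variance".

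For the primary endpoint, section 9.3.2 specifies that "a dummy-coded time variable will be coded with 0 = baseline and 1 for all follow-up visits", plus a group indicator and a group x time term. The group x time coefficient is the treatment contrast to be judged against ±6.5. Section 3 defines the endpoint as the difference between baseline and the average of the follow-up visits, months 3 to 12; the schedule of activities places these at months 3, 6, 9 and 12.

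No part of section 9 says whether the patient effects are an intercept alone or also include an effect of time. No residual covariance, robust standard error or sensitivity analysis is given for this model. Section 9.3.3 reuses the approach for POEM, DLQI/CDLQI and EQ-5D. vIGA is assigned to generalized estimating equations and is outside this point.

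**The concern.** A patient random intercept with independent residuals imposes one variance on all five visits and one correlation on all pairs of visits. Baseline is then assumed to correlate with each follow-up as strongly as the follow-ups correlate with one another. If patients differ in how much they change, that is false. The model then takes the error of the change contrast largely from the scatter among a patient's follow-up visits and misses most of the variation in response between patients.

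Some heterogeneity is to be expected here. The trial enrols from age 1 upward and across all severities, and change is measured in EASI points. Even an equal percentage improvement in everyone would produce unequal point changes.

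In an equivalence trial, a standard error that is too small helps the hypothesis the trial hopes to confirm: a narrower interval fits inside ±6.5 more easily.

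**Working it through.** **Inputs from the documents.** Margin ±6.5 (9.1, 9.3.2); one-sided level 0.05 and 80% power (9.1); SD and attrition "given the range of SD (15-20), with anticipated 15% attrition" (9.1); 300 patients randomized 1:1 (5.4.1, 9.1); one baseline and four follow-ups.

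**The plan's own figure.** For a single one-sided comparison of two means at SD 20, n per arm = 2 × 20² × (1.645 + 0.842)² / 6.5² = 117.1, so 118 per arm and 236 in total. 236 × 1.15 = 271.4, which gives the stated 272. No within-patient correlation enters this calculation, and the plan does not say whether 15 to 20 is the SD of a score or of a change. It therefore cannot settle the covariance question.

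**Model for the check.** Score = patient intercept + patient-specific response (variance τ²) at every follow-up + residual (variance σ²).

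- True per-patient variance of (mean of four follow-ups − baseline): τ² + σ²(1 + 1/4) = τ² + 1.25σ².
- Variance that a random-intercept model attributes to it: the pooled within-patient variance is σ² + τ²/5, so 1.25(σ² + τ²/5) = 1.25σ² + 0.25τ². Three quarters of τ² is lost.
- SE ratio = √[(1.25σ² + 0.25τ²)/(1.25σ² + τ²)].
- False equivalence at a true difference of 6.5 = Φ(−1.645 × SE ratio).

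| τ²/σ² (assumed) | Model / true variance (σ² = 1) | SE ratio | False equivalence |
|---|---|---|---|
| 0 | 1.25 / 1.25 | 1.00 | 5.0% |
| 0.25 | 1.3125 / 1.50 | 0.94 | 6.2% |
| 0.5 | 1.375 / 1.75 | 0.89 | 7.2% |
| 1 | 1.50 / 2.25 | 0.82 | 9.0% |
| 2 | 1.75 / 3.25 | 0.73 | 11.4% |

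**Simulation.** REML fits, 300 patients, 15% monotone dropout, SD of change 20, 1,000 to 2,000 runs per case. For τ²/σ² = 0, 0.5, 1 and 2, the random-intercept model gave 4.5%, 7.4%, 9.2% and 12.0%. Adding a patient random effect of the 0/1 time term gave 4.4%, 4.6%, 5.0% and 5.3%. At a ratio of 1, the intercept-only model reported a mean SE of 1.94 against an empirical SD of 2.38.

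**Other covariance patterns, all assumed.** Write r0 for the baseline-to-follow-up correlation and r1 for the correlation between follow-ups. The true variance and the random-intercept variance follow from the same contrast.

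- Equal SDs, r0 = 0.5, r1 = 0.7: true 0.775, model 0.475, SE ratio 0.78, 9.9%.
- AR(1) only, correlation 0.2 to 0.8 between adjacent visits: 5.6% to 8.1%.
- r0 = r1 = 0.6, follow-up SD 30% below baseline: 9.8%.
- r0 = r1 = 0.6, follow-up SD 30% above baseline: true 0.623, model 0.790, SE ratio 1.13, 3.2% (conservative).
- r0 = 0.5, r1 = 0.6, follow-up SD 30% above baseline: 5.3%.

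**The case against.** The strongest reply is that the plan does not say intercept only. A patient random effect of time fits its wording, and that model holds about 5%. This stands: a reader might infer that the plan prescribes a wrong model, and the text does not go that far. Still, the only stated purpose of the patient effects concerns patient-level variables, the site effects beside them describe shifts in level, and variation in change is never mentioned. An analyst who fits intercepts only would be following the plan. Estimating intra-individual variance, the advantage the plan claims for the model, does not supply the between-patient variance in response.

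A reader might also infer that the error rate roughly doubles. That needs a response variance of about 1.5 times the residual variance (10.3%), and the documents give neither quantity. Milder heterogeneity gives 6% to 7%.

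Nor can the interval be called too narrow as a fact. The direction depends on the data, as the 3.2% case shows. One also cannot assume that care begins only after baseline: section 5.1 admits patients already established with a provider, so follow-ups need not be much more alike than they are to baseline.

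Finally, the one-sided 0.05 level appears only in the sample-size section. Section 9.3.2 gives no interval rule. Under a 95% interval the nominal rate is 2.5%, and the r0 = 0.5, r1 = 0.7 case becomes Φ(−1.96 × 0.783) = 6.2% instead of 9.9%.

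**Conclusion.** The point holds as an unresolved specification that affects the primary error rate. If the model is fitted as patient and site intercepts with the pooled 0/1 time term, false equivalence at the 6.5 margin is about 7% to 11% for response variance 0.5 to 2 times residual variance, and 5% with no heterogeneity. It can fall below 5% when follow-up variance exceeds baseline variance while correlations stay uniform. These figures rest on assumed variances and on the one-sided 0.05 level of section 9.1. Nothing in section 9 corrects the problem if it arises, and leaving the structure open allows the choice to be made after the data are seen. This is a cheap improvement, not a demonstrated failure of the trial.

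**What to change.** In 9.3.1 and 9.3.2, specify one of these for the primary model:

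1. A patient random intercept plus a patient random effect of the baseline/follow-up indicator, with an unstructured 2x2 covariance, fitted by REML. This keeps the pooled 0/1 term and gave 4.4% to 5.3% in the simulation.
2. Categorical visits with an unstructured within-patient covariance in place of the patient random effect, and an equal-weight contrast of months 3, 6, 9 and 12 against baseline. This is more general. Option 1 cannot represent the 3.2% pattern, whose implied response variance is negative (baseline variance 1: 1.014 − 2 × 0.78 + 0.324 = −0.222), so it would stay conservative there.

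Do not combine an unstructured covariance with the pooled 0/1 term. Generalized least squares would then weight the visits unequally: with AR(1) correlation 0.6 the weights for months 3, 6, 9 and 12 are 0.74, 0.06, 0.06 and 0.14. That no longer targets the average defined in section 3.

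Apply the same specification to POEM, DLQI/CDLQI and EQ-5D. The cost is a few sentences and no new data. The downside is a usually wider interval, and so less power than an intercept-only fit would appear to give.
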